4.4 Supportive care guidelines

- Prophylactic use of granulocyte growth factors is not permitted. Use of these hematopoietic factors for grade 4 myelosuppression associated with infection or bleeding is permitted at the discretion of the treating physician and according to guidelines of the American Society of Clinical Oncology. Use of granulocyte growth factor support after neutropenic fever as a secondary prophylaxis is allowed per treating physician discretion.
- Use of erythropoietin is allowed at the discretion of the treating physician.
- Blood transfusions are allowed at the discretion of the treating physician.
- For management of treatment-related side effects, the use of standard supportive care including anti-emetics, intravenous hydration, and analgesics is strongly encouraged and will be decided upon by the treating physician.

4.5 Concomitant medications

- Patients may not receive any other anticancer therapy while on study, including immunotherapy. Patients may not receive any other clinical investigational drug.
- If nausea, vomiting, or diarrhea occurs, effective symptomatic treatment can be initiated. For diarrhea, loperamide (Imodium®) should be used as standard therapy.

4.6 Duration of therapy

Therapy will continue per protocol until any of the following conditions occur

- Disease progression in treated lobe.
- Intercurrent illness that prevents further administration of treatment.
- Unacceptable adverse events.
- Patient decides to withdraw from study.
- General or specific changes in the patient's condition which render the patient unacceptable for further treatment in the judgment of the investigator.
- Judgment of the treating physician that further therapy is unlikely to be of benefit to the patient

4.6.1 Patient withdrawal

Patients may be withdrawn from the study by the investigator or terminate their participation prematurely based on the following:

- Post-consent determination of ineligibility.
- Lack of therapeutic efficacy, as evidenced by progression of treated intra-hepatic disease (progression of untreated liver metastasis or extra-hepatic disease will not be considered failure of therapy). In the latter cases termination of the protocol will be determined according to section 8.1.2. For protocol purposes the patient will be classified based on the response rate of his treated liver lesions using RECIST criteria (as outlined in section 8.1).
- Interval down staging of target lesions such that the patient would be an acceptable candidate for surgical resection.
- Physician's judgment following an adverse event or unacceptable toxicity.
- Termination by the Sponsor, or a regulatory authority.
- Patients that require radiation therapy for local palliative purposes.

Any other reason for withdrawal that the treating physician or patient indicates is in the overall best interest of the patient.

4.7 Follow Up

Copyright© 2015 Fox Chase Cancer Center® Clinical Trials Operations. All rights reserved. Version Date 02/27/2017

The patient will be clinically evaluated approximately 30 days after completion of the trial. Telephone follow up at 3 month intervals for up to 2 years for survival and toxicity monitoring will be conducted. At treating physician discretion, patients may be followed more frequently for toxicities felt to be treatment-related.

5.0 Adverse Events

5.1 Definitions

5.1.1 Adverse Events (AE) is any unfavorable and unintended sign (including an abnormal laboratory finding), symptom or disease temporally associated with the use of a medicinal (investigational) product, treatment or procedure regardless of whether it is considered related to the medical treatment or procedure (*NCI CTEP Guidelines March 28, 2011*).

5.1.2 Serious Adverse Event (SAE) is an AE that is fatal or life threatening, requires inpatient hospitalization or prolongation of existing hospitalization (for > 24 hours), persistent or significant incapacity or substantial disruption of the ability to conduct normal life functions, or is a congenital anomaly/ birth defect, or results in any important medical event that may not result in death, be life threatening, or require hospitalization may be considered an SAE when, based upon appropriate medical judgment, may jeopardize the subject and may require medical or surgical intervention to prevent any of the above outcomes. A “life-threatening” adverse event places the patient at immediate risk of death in the judgment of the investigator or sponsor.

5.1.3 Severity Rating

The investigator will evaluate the severity of each adverse event. NCI Common Terminology Criteria for Adverse Events (CTCAE v.4.0) or study specific toxicity tables provided in the protocol define severity. If not included in CTCAE v.4.0, severity is expressed in numerical grade using the following definitions:

1. Grade 1: Mild-asymptomatic or mild symptoms; clinical or diagnostic observations only; intervention not indicated.
2. Grade 2: Moderate-minimal, local or noninvasive intervention indicated; limiting age appropriate instrumental ADL.
3. Grade 3: Severe-severe or medically significant but not immediately life-threatening; hospitalization or prolongation of hospitalization indicated; disabling; limiting self-care ADL.
4. Grade 4: Life-threatening consequences; urgent intervention indicated.
5. Grade 5: Death related to AE

5.1.4 Attribution/Relationship to study drug

1. Definite – clearly related
2. Probable – likely related
3. Possible – may be related
4. Unlikely – doubtfully related
5. Unrelated – clearly not related

5.1.5 Expectedness

An Expected Adverse Event is one where the specificity or severity is consistent with the current information available from the resources.

An Unexpected Adverse Event is one where the nature, severity, or frequency of the event is related to participation in the research is not consistent with either:

1. The known or foreseeable risk of adverse events associated with the procedures involved in the research that are described in (a) the protocol-related documents, such as the IRB-approved research protocol, any applicable investigator brochure, and the current IRB-approved informed consent

document, and (b) other relevant sources of information, such as product labeling and package inserts:

OR

2. The expected natural progression of any underlying disease, disorder, or condition of the subject (s) experiencing the adverse event and the subjects(s) predisposing risk factor profile for the adverse event.(OHRP Guidance on reviewing unanticipated problems 2007)

5.2 Recording and Reporting Responsibilities**5.2.1 Investigative site recording responsibilities:**

1. Upon identification of an AE or SAE, the site investigator will utilize the above definitions to properly classify the event. Each category listed above must be recorded for each event.
2. All AEs and SAEs will be recorded in the “AE case report forms” (CRF) and in progress reports with details about the grade and attribution of each episode, action taken with respect to the study drug, and the patient’s outcome will be recorded in the CRF. All events will be recorded on case report forms for the duration of the study until they resolve.
3. All SAEs will be recorded on the FDA MedWatch form 3500a. After submitting the initial report it may be necessary to submit follow up reports should the event require further investigation.

5.2.2 Investigative site reporting responsibilities:

1. The investigator/ site is responsible to report all SAEs that occur on or after the first day of study treatment and up to 30 days after the last study treatment to the Sponsor within 24 hours of becoming aware of the event.
2. Each investigator is responsible to report all AEs/SAEs to their local IRB following guidelines set by that IRB. The FCCC OCR reserves the right to request an event be reported to the IRB at their discretion. Copies of events reviewed by email to [contact].
3. If the investigator or IRB feels the event warrants a revision to the informed consent that was not already initiated by the OCR, draft revisions will be made in track changes and submitted to the OCR for consideration. Any consent revisions must receive OCR approval **prior** to submission to the IRB.
4. Any investigator who is in doubt of whether a particular AE needs to be reported is directed to call Study Monitor for confirmation with the Sponsor-Investigator.
5. If the results of an investigator or OCR investigation show an adverse event not initially determined to be reportable is so reportable, the investigator will report the event following the above guidelines based on the date the determination is made.
6. Copies of all related correspondence and reporting documents must be submitted to the ISRU and will be maintained in the trial master file.

Participating sites should report events to:

Investigator-Sponsored Research Unit
Office of Clinical Research
Fox Chase Cancer Center
[contact]

5.2.3 Sponsor Reporting Responsibilities:

1. Adverse events which meet all of the following criteria must be reported to all participating institutions for IRB submission within 2 weeks of notification of the event.
 - i. Unexpected (in terms of nature, severity, or frequency) given (a) the research procedures that are described in the protocol-related documents, such as the IRB-approved research protocol and informed consent document; and (b) the characteristics of the subject population being studied;
 - ii. Possibly related to participation in the research (possibly related means there is a reasonable possibility that the incident, experience, or outcome may have been caused by the procedures involved in the research); and
 - iii. Serious (refer to above definition) or otherwise one that suggests that the research places subjects or others at a greater risk of physical or psychological harm than was previously known or recognized.
2. If the adverse event requires modification of the study protocol and informed consent, these changes will be provided to all participating institutions in the form of an amendment from the ISRU for each site's IRB of record along with the report of the adverse event.
3. Copies of all related correspondence and reporting documents will be maintained in a centralized regulatory file for this study within the OCR.
4. SAEs that are related, unexpected, fatal, or life-threatening are reportable through the Food and Drug Administration (FDA) MedWatch program by telephone or fax no later than 7 calendar days after initial receipt of the information. Further information on the timing of submissions are as directed by FDA guidelines (<http://www.fda.gov/medwatch/index.html>). Serious, unexpected events that suggest significant clinical risk will be submitted to within 15 calendar days after initial receipt of this information.

**Food and Drug Administration (FDA)
Center for Devices and Radiological Health
Document Mail Center – W066-G609
[name]
[name] 20993-0002**

In addition, any Medical Device Report (MDR) may be faxed to FDA following approval. A request for approval of facsimile reports can be obtained by calling [contact]

AND

Within 24 hours of becoming aware:

Biocompatibles Inc., a BTG International Group Company
[contact]

Any serious adverse events which occur during the clinical study or within 30 days of receiving the last dose of study medication, whether or not related to the study drug, must be reported.

6.0 DEBIRI formulation and procurement

LC Bead microspheres are produced from a biocompatible polyvinyl alcohol (PVA) hydrogel that contains sulphonate groups which allow the controlled loading and delivery of chemotherapeutic drugs. LC Bead occludes the blood flow to the target tissue and delivers a local and sustained dose of drug direct to the tumor. LC bead is 510K cleared by the FDA for the embolization of hypervasculatized tumors and arteriovenous malformations (AVMs) only. Loading of irinotecan into the LC Bead is considered investigational in the US.

LC Bead is biochemically identical to DC Bead which received CE mark approval in 2003 and is indicated for the treatment of malignant hyper-vascularised tumors and loading with doxorubicin. DC Bead may also be loaded with Irinotecan for the treatment of metastatic colorectal cancer.

The intention of this study is to use LC Bead loaded with irinotecan for the purpose of: embolization of vessels supplying malignant metastatic tumor(s) and delivery of a local, controlled, sustained dose of irinotecan to the tumor(s)

LC Bead comprise a range of hydrogel microspheres that are biocompatible, hydrophilic, non resorbable and precisely calibrated. Various beads sizes are available for use ranging from 70 to 900 μ m. In this study we will utilize the smallest size beads (70-150 μ m- Yellow-black label – M1), which are thought to have improved penetration to the tumor and therefore more targeted drug delivery.

Upon loading with irinotecan, LC Bead undergo a slight decrease in size, up to 30% when loading at 50mg/ml. At the time of use, LC Bead will be mixed with irinotecan according to the instructions for loading. LC Beads are suitable for loading irinotecan Solution (20mg/ml) ONLY. With the use of M1 LC beads it is recommended that the user will ensure that the size is appropriate for the intended vasculature. In addition, patients should be carefully monitored for signs of non-target embolization such as hypoxia or CNS changes. Finally the user should consider upsizing of the beads if angiographic evidence of embolization does not appear quickly during delivery.

Drug loading instructions: These are the loading instruction for all dose levels on this study.

1. Remove as much saline as possible from a vial of LC Bead using a syringe with a small gauge needle.
2. Using a syringe and needle add the appropriate amount of Irinotecan solution (solution concentration of 20mg/ml) directly to the vial of LC Bead, as outlined in the table below:

Irinotecan dose	Amount to be added to LC beads
50mg	2.5ml
75mg	3.75ml
100mg	5ml

3. Agitate the LC Bead / Irinotecan solution gently to encourage mixing then allow standing. The beads will turn a turquoise color as the loading progresses.
4. The minimal incubation time is 2 hours for 98% absorption, but may be up to 5 hours for 100% absorption.
5. Prior to use, transfer the LC Bead loaded with irinotecan to a syringe and expel the excess supernatant using a filter needle. Add 5ml sterile water, in order to minimize irinotecan elution, and add 10-20 cc of contrast media per 1ml/cc of irinotecan loaded beads. Invert the syringe gently to obtain an even suspension of DC Bead.

LC Bead loaded with irinotecan is physically and chemically stable for up to 14 days if stored in a fridge at 2-8°C or 4 hours at room temperature in the absence of non-ionic contrast media. However the allocation of a shelf-life longer than 4 hours at room temperature or 24 hours if stored in the fridge is the responsibility of the user and dependent upon the use of controlled aseptic conditions for preparation. The irinotecan loaded bead solution will be mixed with non-ionic contrast only at the time of injection into the patient via a properly placed catheter or microcatheter.

In this protocol the beads will be loaded within 2 hours of the procedure. Discard any unused LC Bead loaded with irinotecan.

7.0 Study Calendar

All pre-study/baseline evaluations except serum pregnancy test may be performed up to 28 days prior to registration. A timetable of relevant assessments is provided in the table below for uni-lobar and bi-lobar disease (all tests can be performed within ± 2 days of this schedule). This timetable contains the schedule for two treatments 3 weeks apart followed by CT on week 8. The schedule can be repeated for additional treatment in appropriate cases (section 4.2.1).

Based on experience from previous studies using DEBIRI there exists a risk of post procedure transient edema, which may confound the response evaluation by RECIST criteria. In case of disease progression on week 8 imaging the patient will be followed with repeat CT at 12 weeks to rule out the possibility of edema accounting for the progressive disease.

Study Calendar

	Pre-Study	Day 1 (± 2) ⁱ	Day 2 ⁱ	Day 8	Day 15	Day 22 (± 2) ⁱ	Day 23 ⁱ	Day 29	Day 36	Day 57	EOT ^h	Follow Up for Survival ^j
Planned treatment (Unilobar/dominant lesion in bilobar disease) ± 2 days ^a		X				X						
Informed consent	X											
Demographics	X											
Medical History ^b	X											
Concurrent meds	X	X-----X										
Physical exam ^b	X		X	X	X	X	X	X	X		X	
Height	X											
Performance Status	X					X					X	
CBC w/diff ^c	X		X	X	X	X	X	X	X		X	
Serum chemistry ^c	X		X	X	X	X	X	X	X		X	
CEA ^d	X									X	X	
PT/INR/PTT ^e	X					X					X	
Adverse Event Evaluations		X-----X										
CT scan of the chest abdomen & pelvis ^f	X									X ^K		
B-HCG ^g	X											
Hepatic angiogram		X										

a. Patients with unilobar disease will be treated on day 1 ± 2 days and 3 weeks later on day 22 ± 2 days with CT 8 weeks after the initial treatment. Patient with bilobar disease will receive treatment to the dominant lobe on day 1 ± 2 days and 3 weeks later on day 21 ± 2 days with CT 8 weeks after the initial treatment. Patients without evidence of progression will be candidates for treatment of the non-treated lobe for 2 treatments 3 weeks apart.
b. Medical history and physical examination will be obtained prior to each treatment according to the treatment schedule (± 2 days). Pre-treatment medical history can consist of interval history.
c. CBC and Chemistry are to be obtained on the day before treatment (± 2 days), and every week while on the study (± 2 days). Additional blood tests should be performed per the discretion of the treating physician. Blood work obtained within ± 2 days may be used.
d. CEA evaluation will be obtained at the beginning of the study and with each imaging evaluation.
e. PT/INR/PTT only required prior to each procedure.
f. Additional imaging may be obtained at discretion of treating physician (e.g. MRI, PET scan, etc.). Alternative imaging of liver (ie MRI in place of CT scan) is acceptable when preferred by treating physician. MRI of the liver may be used as a substitute for a CT scan for patients with creatinine 1.5-2.0 who are at risk for contrast induced nephropathy. Diabetic patients treated with medications from the biguanides family such as Metformin would be required to hold their medicine for 1 day before and 2 days after their scheduled CT scan.
g. Serum pregnancy test (women of childbearing potential) within 72 hours before treatment.
h. Off-study evaluation. Two consecutive measurements taken at least 4 weeks apart must be used to document partial or complete responses in patients meeting these criteria with measurable disease. Follow-up details are available in section 4.7.
i. Following the procedure the patient will be admitted for overnight observation. On day 1 post treatment blood work including CBC and CMP will be obtained along with physical examination.
j. Patients will be followed up for overall survival status. Medical evaluation is NOT required to determine status. The patient will be clinically evaluated approximately 30 days after completion of the trial. Telephone follow up at 3 month intervals for up to 2 years for survival and toxicity monitoring will be conducted. At treating physician discretion, patients may be followed more frequently for toxicities felt to be treatment-related.
k. Patients who demonstrate progression with their Day 57 (week 8) CT scan should have a repeat CT scan at week 12 to rule out inflammation as a source of tumor enlargement.

8.0 Measurement of Effect

Although response is not the primary endpoint of this trial, patients with measurable disease will be assessed by standard criteria. For the purposes of this study, all patients will be evaluated for response 8 weeks following the administration of DEBIRI, response rate will be calculated based on the treated lobe only. In addition to a baseline scan, confirmatory scans must be obtained at least 4 weeks following the initial documentation of complete or partial response. In cases of disease progression at 8 weeks, repeat CT will be done at 12 weeks to exclude the possibility of treatment related transient edema accounting for disease progression.

Definitions

Response and progression will be evaluated in this study using the international criteria proposed by the Response Evaluation Criteria in Solid Tumors (RECIST) Committee version 1.1 (50, 51) . RECIST 1.1 limits the number of measurable lesions in an organ to 2 and the total number of measurable lesions to 5. Since response is being evaluated in this study only in the treated lobe of the liver, we will measure response on up to 5 total lesions in that lobe of liver.

Patients must have at least one measurable lesion, defined as >20mm using CT or MRI, or >10mm using spiral CT. Where disease is restricted to a solitary lesion, its neoplastic nature must be confirmed by cytology/histology.

Baseline measurements must be taken not more than four weeks prior to commencement of treatment. The same measurement technique (CT/MRI) must be used at baseline and follow up. No more than 5 target lesions in the liver will be identified. Those with the largest diameters should be included.

A sum of the longest dimension (LD) for all target lesions will be calculated and reported as the baseline sum LD. The baseline sum LD will be used as reference to further characterize the objective tumor response of the measurable dimension of the disease. Change on the sum of these dimensions affords some estimate of change in tumor size and hence therapeutic efficacy.

8.1 Response Criteria

8.1.1 Evaluation of target lesions

Complete Response (CR):	Disappearance of all target lesions, or disappearance of arterial enhancement in the target lesion
Partial Response (PR):	At least a 30% decrease in the sum of the longest diameter (LD) of target lesions, taking as reference the baseline sum LD.
Progressive Disease (PD):	
 At least a 20% increase in the sum of the LD of target lesions, taking as reference the smallest sum LD recorded since the treatment started. The appearance of one or more new lesions. Death due to disease without objective evidence of progression

Stable Disease (SD):	Neither sufficient shrinkage to qualify for PR nor sufficient increase to qualify for PD, taking as reference the smallest sum LD since the treatment started
Symptomatic Deterioration	Is defined as a global deterioration in health status attributable to the disease requiring a change in therapy without objective evidence of progression.
In evaluable for Response	Is defined as having no repeat tumor assessments following initiation of study therapy for reasons unrelated to symptoms or signs of disease

Target Lesions	Non-Target Lesions	New Lesions	Overall Response	Best Overall Response when Confirmation is Required*
CR	CR	No	CR	>4 wks. Confirmation
CR	Non-CR/Non-PD	No	PR	
CR	Not evaluated	No	PR	
PR	Non-CR/Non-PD/not evaluated	No	PR	
SD	Non-CR/Non-PD/not evaluated	No	SD	Documented at least once ≥ 4 wks. from baseline
PD	Any	Yes or No	PD	no prior SD, PR or CR
Any	PD*	Yes or No	PD	
Any	Any	Yes	PD	

* See RECIST 1.1 manuscript for further details on what is evidence of a new lesion (51).
 * In exceptional circumstances, unequivocal progression in non-target lesions may be accepted as disease progression.

8.1.2 Progressive disease outside of the liver:

For protocol purposes new or increasing lesions outside of the liver will not be considered progressive disease. However, the protocol will be discontinued in the following cases in which the extent of disease limits further benefit of liver-directed treatment:

- Diffuse pulmonary disease
- Diffuse peritoneal carcinomatosis
- Diffuse lymph node involvement
- Diffuse bone metastases with bone marrow compromise
- New metastatic disease resulting in organ dysfunction, or intractable pain.

The treating physician may elect to terminate participation in this protocol in other cases in which alternative therapy is indicated.

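### Complete response can be met by lost arterial enhancement alone under a RECIST 1.1 label, and the plan does not rank that against size-based stable or progressive disease

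*Combined protocol and SAP*

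**What the plan says.** Section 8.0 names the criteria as those of the "Response Evaluation Criteria in Solid Tumors (RECIST) Committee version 1.1" and sets the measure: "A sum of the longest dimension (LD) for all target lesions will be calculated and reported as the baseline sum LD". It explains its adaptations. Response is judged in the treated lobe only, and "we will measure response on up to 5 total lesions in that lobe of liver". After apparent progression at week 8, "repeat CT will be done at 12 weeks to exclude the possibility of treatment related transient edema". Section 8.1.2 adds one more: "For protocol purposes new or increasing lesions outside of the liver will not be considered progressive disease". None of these mentions enhancement. Section 4.1.2 also points to RECIST as set out in section 8.0.

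Section 8.1.1 gives the target-lesion definitions. CR is "Disappearance of all target lesions, or disappearance of arterial enhancement in the target lesion". PR is a fall of at least 30% in sum LD from baseline. The growth part of PD is a rise of at least 20%, "taking as reference the smallest sum LD recorded since the treatment started"; new lesions and death due to disease also count as PD. SD is what remains between PR and PD by size.

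On confirmation, section 8.0 says that "confirmatory scans must be obtained at least 4 weeks following the initial documentation of complete or partial response". Section 8.2 starts duration of response when CR or PR criteria are first met. Section 9.1.2 assigns each patient a single response category.

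**The concern.** Every target-lesion category that rests on measurement uses sum LD, except for one alternative inside the best category. A patient whose lesions have not shrunk, or have grown, can therefore be recorded as a complete responder in a rate presented as RECIST 1.1. The same scan can also satisfy two categories when only one may be assigned, so two readers could follow the plan correctly and disagree.

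Response rate is a secondary objective, and section 1.5 says the data will be used to develop future trials. The duration-of-response clock could start without any shrinkage. If CR were allowed to outrank growth, time to progression could lengthen as well. A smaller ambiguity is that the first CR alternative refers to all target lesions while the second uses the singular, so with up to 5 lesions it is not explicit that every one must lose enhancement.

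**Working it through.** The plan states no response rate, threshold or sample size for response, so there is no figure of its own to reproduce. The check has three parts.

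**1. Do the categories overlap?** Inputs are the definitions in section 8.1.1. Take a baseline sum LD of 100 and enhancement lost at the week-8 scan. Assume no scan in between, so baseline is the reference for both shrinkage and growth.

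| Sum LD at week 8 | Change | By size | By the enhancement alternative |
|---|---|---|---|
| 70 | -30% | PR | CR |
| 100 | 0% | SD | CR |
| 120 | +20% | PD | CR |

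The first row affects the CR rate but not the response rate. The other two turn a non-response into a possible response. With non-target disease neither CR nor PD and no new lesions, the overall-response table gives PR if the target result is entered as CR, SD if entered as SD, and PD if entered as PD. The table ranks new lesions and non-target PD above any target result. It takes the target category as given, so it cannot resolve a conflict within the target lesions.

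**2. Which way does the clause move the rate?** Cross 4 size categories, enhancement lost or not, 4 non-target states (CR, neither CR nor PD, not evaluated, PD) and new lesion or not: 4 × 2 × 4 × 2 = 64 combinations. Where the table has no row (target PR or SD with non-target CR), the target category is carried forward as an assumption. Compare with a size-only CR.

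- The clause can matter only if enhancement is lost, there is no new lesion and non-target disease is not PD: 4 × 3 = 12 combinations.
- Size CR and size PR (6 combinations) are responses either way.
- Size SD (3 combinations) moves to CR or PR.
- Size PD (3 combinations) moves to CR or PR if CR outranks PD, and otherwise stays PD.

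If CR outranks PD, 6 move up, 0 down and 58 do not change. If PD outranks CR, 3 move up, 0 down and 61 do not change.

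For confirmed response, consider two scans with the target category taken as the overall category. Each scan has 4 × 2 = 8 states, of which 4 are responses by size. With the clause, 6 are responses if CR outranks PD, or 5 if PD outranks CR. If any response followed by any response confirms, the gain is 6² - 4² = 20 sequences, or 5² - 4² = 9, with none lost. If CR followed by PR is not accepted as confirmed, one sequence is lost: PR by size on both scans, with enhancement lost on the first and back on the second.

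**3. How large is each reclassification?** It adds 100/n percentage points. The candidate denominators come from section 9.0, assuming that all these patients have measurable disease.

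| n | Source | Points per patient |
|---|---|---|
| 9 | lower accrual limit (no room for the expansion) | 100/9 = 11.1 |
| 20 | 6 at the MTD + 14 expansion | 100/20 = 5.0 |
| 23 | 3 + 3 + 3 + 14 | 100/23 = 4.3 |
| 30 | upper accrual limit | 100/30 = 3.3 |

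The documents give no frequency for lost enhancement without shrinkage. Purely for illustration, 0 to 4 such patients (an assumption) would add 0 to 20.0 points at n=20, 0 to 17.4 at n=23 and 0 to 13.3 at n=30.

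**The case against.** The strongest reply is that the enhancement alternative may be deliberate. Section 7.0 warns that edema after the procedure can confound size-based RECIST, and a measure less tied to size could be a sensible response to that. This stands in part: the documents do not show that a size-only rate is the better measure. But they do not explain the clause as an adaptation, as they do the others, and a deliberate combined measure would still need its own label and a rule for the overlaps.

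A second reply is that confirmation at 4 weeks or more protects the rate. It may reduce the effect, but the confirmatory scan can satisfy the same alternative.

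A third is that little depends on this. That is right about scale: no hypothesis or stopping rule uses response, and section 9.0 works with DLTs only.

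Some stronger readings are tempting but not supported:

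- That the plan has no precedence rule at all. The table does rank new lesions and non-target PD above a target CR; the gap lies within the target lesions.
- That the confirmed response rate can never fall because of the clause. That depends on how CR followed by PR is treated.
- That PR and PD collide in any case, for example with baseline 100, smallest 40 and now 60 (-40% from baseline, +50% from the smallest). Section 8.2 largely handles this by ending response at progression measured from the smallest value.
- That section 1.3 shows response and enhancement being kept apart in a previous DEBIRI trial. It does not say how response was defined there.

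**Conclusion.** The point holds as a fault in a secondary-endpoint definition. Followed as written, section 8.1.1 can count a patient without shrinkage as a response in a rate labelled RECIST 1.1, and it leaves CR against SD and CR against PD unresolved within the target lesions. The upward direction is exact at each assessment; for confirmed response it rests on CR followed by PR being accepted.

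The effect per reclassified patient is known once n is fixed, but the number of such patients is not, so a reader should not infer that the reported rate will be inflated by any particular amount. The plan also does not say whether response will be pooled over dose levels or reported at the MTD, which is why several values of n are shown. Response rate and duration of response are affected, and time to progression possibly. MTD determination, accrual and the toxicity rule are not.

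**What to change.** For the rate labelled RECIST 1.1, define CR without the enhancement alternative. Report loss of arterial enhancement in all target lesions as a separate, labelled descriptive endpoint, with the number of patients in whom it could be assessed. If the sponsor prefers to keep a combined measure, label it as modified criteria and show it beside the size-only rate, with responses split by the route through which they were met.

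Add one sentence, limited to endpoint classification: size-based PD in target lesions, subject to the 12-week repeat CT already planned, is not overridden by loss of enhancement. Progression in the treated lobe also drives treatment decisions in sections 4.1.2 and 4.6. The sponsor should reconcile those passages separately; nothing is proposed here about them.

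The cost is one clause, one sentence and one descriptive table. No extra patients are needed, and no extra scans for the size-based rate. The downsides are that the reported CR and response rates may be lower, that the size-based rate stays exposed to edema, and that enhancement data may be incomplete because the study calendar specifies no arterial phase and allows MRI in place of CT.
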